## 3. Method

The study is a randomized, controlled, multicenter study in patients with liver malignancies treated at the four Danish liver surgery centers (Rigshospitalet, Odense, Århus and Aalborg). Patients with one or more liver tumor suitable for ablation as primary treatment, but not amenable for percutaneous ablation will be randomized between laparoscopic and open ablation. Opaque envelopes with patient numbers containing the randomization sequence will be opened after informed consent has been obtained. We plan to include 80 patients with 40 patients per arm. Patients will be randomized 1:1 (see below). Randomization will be stratified on center level to ensure comparable populations between the groups within each center.

Due to perioperative findings, the treatment to which the patient is randomized to may be considered not feasible or inappropriate, e.g. due to insufficient visualisation of tumor or findings that warrant a different treatment strategy. In these cases, the treatment strategy is based on the surgeons preferences. In laparoscopic cases, a minimally invasive approach should be maintained if possible, e.g. by combining laparoscopy with percutaneous ablation needle placement.

Ninety days after the procedure, the patient chart will be evaluated to register patient characteristics and outcomes. Moreover, at one month all patients will receive a CT-scan to evaluate success rate (complete ablation response). The CT-scan is part of standard of care, it is assessed by an experienced radiologist, and it is not part of this study. Before surgery and one month after, health related quality of life (HRQoL), the psychological burden and level of recovery will be assessed. Open ablation is standard of care. Thus, the intervention group will receive a treatment with assumed fewer complications and similar success rate.

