#### Feasibility and timeline

The project will be carried out at the four Danish liver surgery centers (Rigshospitalet, Odense, Århus and Aalborg). Office space and facilities will be provided. The project group includes experienced researchers and surgeons specialized in liver surgery.

In 2019 and 2020, approximately 45-50 patients each year with liver malignancies were treated solely with ablation during open surgery in Rigshospitalet. The majority of these patients may be included in the present study. Approximately half of the procedure in Denmark are performed at Rigshospitalet

with the remaining distributed between the others centers in Odense, Århus and Aalborg. Thus, we expect that all patients for this study can be recruited in approximately 1.5 years (see sample-size calculation). The procedures will be performed by experienced liver surgeons to maintain the technical skills required.

The project will form the basis of a PhD project and results will be published in international peer-reviewed scientific journals. The PhD-student will handle inclusion at Rigshospitalet, follow-up, data collection, statistical analyses, and writing of three papers. A PhD-student will be hired through the job portal of Copenhagen University and sundhedsjobs.dk. Based on interviews, we will hire the best qualified candidate. The study group members in Odense, Århus and Aalborg will handle inclusion of patients and perform the procedures in their own center. The study has been funded from The Danish Cancer Society “Knæk Cancer”, which covers three year salary for a PhD-student and a 20% research position designated to the primary investigator.

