## 5. Patients

Inclusion criteria: one or more tumors not amenable to percutaneous ablation, age > 18 years, signed informed consent, diagnosis of primary liver cancer or liver metastases from any primary tumor, and tumor suitable for ablation as primary treatment

Exclusion criteria: ablation performed in conjunction with resection, patients who cannot cooperate with the study, and patients who do not understand or speak Danish

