## 12. Recruitment of subjects and informed consent

The participants are among the patients who are already referred for treatment of a liver tumor at the included centers. These patients are identified by a clinician, and informed about the possibility of being informed about the project.

After a joint decision between a specialist and the patient about ablation of a liver tumor not amenable for percutaneous ablation, typically at the first visit to the surgical outpatient clinic, and after it has been ensured that the inclusion and exclusion criteria are met, the patient will be oriented about the project and offered written and oral information.

Interested patients are informed orally and given written participant information. The patient will be offered an in-depth interview during the day. During the interview, the patient will receive verbally sufficient information about the purpose and structure of the study, as well as potential risks and disadvantages. The patients will be informed that participation is voluntary and that they can withdraw from the study at any time, without this having an impact on their further progress in the department. They will also be informed that they may be withdrawn from the study at the discretion of the investigator responsible for the study.

The patients will also be informed about the treatment they will be offered if they choose to say no to participating, and they will also be informed that all data will be treated confidentially.

A copy of the information and signed declaration of consent will be given to the patient and a copy will be kept in the medical record. Current regulations from the Scientific Ethics Committee regarding informed consent will be followed.

It is the responsibility of the primary investigator that all patients receive oral information, so that it is ensured that the patient is completely aware of all aspects of participation in the study. The patient can withdraw his consent to participate in the study at any time. If the patient decides to do this, it will not impair his or her relationship with investigators or other staff, and the patient will continue to receive the best treatment the department can offer.

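### Concealment of the next arm is not secured by the envelope procedure as described, mainly at the three centres where the same people include patients and operate

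*Combined protocol and SAP*

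**What the plan says.** Section 3 (Method) describes allocation in one sentence: "Opaque envelopes with patient numbers containing the randomization sequence will be opened after informed consent has been obtained". The ratio is 1:1, and "Randomization will be stratified on center level to ensure comparable populations between the groups within each center". Method points forward for more on randomisation, but the later text on treatment and follow-up only repeats the ratio and names the two arms.

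The Feasibility and timeline section assigns the roles. For three centres: "The study group members in Odense, Århus and Aalborg will handle inclusion of patients and perform the procedures in their own center". For the fourth: "The PhD-student will handle inclusion at Rigshospitalet, follow-up, data collection, statistical analyses, and writing of three papers". It adds: "Approximately half of the procedure in Denmark are performed at Rigshospitalet".

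Entry depends partly on judgement. Section 5 requires that the tumour cannot be treated percutaneously and is suitable for ablation, with no objective rule for either, and it excludes "patients who cannot cooperate with the study, and patients who do not understand or speak Danish". Section 12 places the clinical decision before the patient hears about the study: "After a joint decision between a specialist and the patient about ablation of a liver tumor not amenable for percutaneous ablation".

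The available text does not say whether envelopes are sealed or used in strict order, who generates the list, who holds the envelopes, whether openings are logged, or whether blocks are used and of what size.

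**The concern.** Concealment means that nobody who influences entry knows the next arm before the patient is in. It is separate from blinding the surgeon, which is not possible here, and from how long before surgery the envelope is opened.

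Three features make concealment matter more in this plan. Once a patient has been operated on, the arm is known locally. The strata are centres, and three of them share about half of the procedures, so each stratum is small. At those three centres the person who includes the patient also operates, and entry criteria leave room for judgement.

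Someone who knew or guessed the next arm could offer the study, delay it, or call a tumour unsuitable according to how difficult the case looked. The arms would then differ at entry. Neither the intention-to-treat analysis nor Fisher's exact test in section 4 could correct that.

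**Working it through.** **1. The plan's own figure.** Section 4 (Sample size) gives 60 patients for 45% versus 10%, alpha 5%, power 80%. Two-sided, with mean proportion 0.275:

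- n = [1.960 × √(2 × 0.275 × 0.725) + 0.842 × √(0.45 × 0.55 + 0.10 × 0.90)]² / 0.35² = 24.3 per arm.
- With continuity correction: (24.3/4) × [1 + √(1 + 4/(24.3 × 0.35))]² = 29.8, so 30 per arm and 60 in total. This reproduces.

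The figure does not depend on the concealment method, so no corrected sample size follows. What can be calculated is how much could go wrong under stated assumptions.

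**2. Predictability if blocks were used (assumption; the plan names none).** Past arms at the centre are known, and the recruiter guesses the arm that is under-represented so far in the block. For blocks of 4:

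- Chance of a correct guess at positions 1 to 4: 1/2, 2/3, 2/3, 1. Mean = 2.833/4 = 70.8%.
- Chance that the next arm is certain: 0, 0, 1/3, 1. Mean = 1.333/4 = 33%.

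Enumerating full blocks in the same way:

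| Block size | Certain | Guessed correctly |
|---|---|---|
| 2 | 50% | 75% |
| 4 | 33% | 70.8% |
| 6 | 25% | 68.3% |
| 8 | 20% | 66.6% |

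Without blocking, the correct-guess rate is 50%.

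**3. Spurious difference.** Assume no true effect, a risk of 45% in both arms, and a recruiter who shifts the included patient's risk up or down by d according to the guess. With g the correct-guess rate and f the share of patients at steering centres, the expected gap is 2 × (2g − 1) × d × f. The three combined-role centres are taken as f = 0.5, since Rigshospitalet performs about half of the procedures.

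- Blocks of 4: 2 × 0.417 × d × 0.5 = 0.417d, so 4.2 points for d = 10 and 6.3 for d = 15.
- Blocks of 2: 2 × 0.5 × d × 0.5 = 0.5d, so 5.0 and 7.5 points.

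**4. Effect on the test.** Simulation: 80 patients, centres of 40, 14, 13 and 13 (assumed split), 3,000 trials per scenario, two-sided Fisher test at 0.05. Gaps come out slightly below step 3, partly because small strata end in incomplete blocks.

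| Who steers | Block | d (points) | Spurious difference (points) | Type I error |
|---|---|---|---|---|
| Nobody | 2 or 4 | – | about 0 | about 3.8% |
| Three centres | 4 | 10 | 3.5 | 5.1% |
| Three centres | 2 | 10 | 4.9 | 5.2% |
| Three centres | 4 | 15 | 6.0 | 6.3% |
| Three centres | 2 | 15 | 7.2 | 7.7% |
| All centres | 4 | 10 | 7.8 | 8.4% |
| All centres | 2 | 10 | 9.5 | 10.0% |
| All centres | 4 | 15 | 12.0 | 15.9% |
| All centres | 2 | 15 | 14.6 | 21.0% |

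The simulation error on a rate near 5% is √(0.05 × 0.95/3000) = 0.4 points, so the first decimals carry little weight.

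**The case against.** The strongest reply is that the described procedure can work. Opaque envelopes tied to patient numbers and opened only after consent do conceal the next arm if they are sealed and used in order. Section 12 also has the entry criteria confirmed before the patient is told about the study. A reader might infer that the next arm can be learned, or that envelopes lie open to inspection at each centre. The documents support neither: they do not say where the envelopes are kept, and early opening would breach the stated rule. What stands is narrower. The safeguards that would exclude foreknowledge are not stated, and checking eligibility first does not help if the next arm is already known or guessed.

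The roles should not be overgeneralised. At Rigshospitalet the PhD-student handles inclusion and is not described as operating. A specialist still judges suitability there, and the text does not say whether that person operates.

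The predictability figures come from blocking, not from envelopes. They would apply equally to central allocation with the same known blocks, so central release alone would not close that route.

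A reader might also take a false-positive rate near 21% as the size of the problem. Setting the laparoscopic arm's risk 15 points lower by hand does give 21.2% rejections favouring laparoscopy. With blocks of 4 and steering at the three centres only, however, a 15-point gap needs d = 15/0.417 = 36 points, that is, choosing patients with 9% or 81% risk around a base of 45%. Errors of that order need steering at all centres or actual envelope breaches.

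The direction is open too. The Background regards a minimally invasive approach as especially relevant for high-risk patients. Recruiters who share that view could send sicker patients to laparoscopy and hide a real benefit.

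Finally, some text was not in the copy available, so the omissions are claimed for the available text only.

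**Conclusion.** The concern holds in limited form. Envelopes are the only stated concealment in a trial with no blinding described, three of four centres combine inclusion and operating, and key entry criteria are judgements. Concealment is therefore not secured, mainly at those three centres; that the arm is actually learned is not shown.

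Under steering by guesswork at those centres alone, the spurious difference is about 3.5 to 7 points and the two-sided type I error 5.1% to 7.7%, against 3.8%. This rests on assumed fixed blocks of 2 or 4, an assumed risk shift of 10 to 15 points, and half of the patients coming from those centres. The bias could run either way. The effect is modest, but analysis cannot remove it and prevention is cheap, so the change should be made.

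**What to change.** In section 3 (Method), replace local envelopes by central release. Each arm is issued one patient at a time, only after patient number, centre, eligibility and consent have been irrevocably logged. Keep stratification by centre, and use randomly varying block sizes that are not disclosed to the sites. State who generates the list; this should not be anyone who includes patients or operates.

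The protocol mentions a case report form but no electronic allocation system. If none is available, use sealed, sequentially numbered opaque envelopes, held and logged by existing staff who neither include patients nor operate, with the same rule on block sizes.

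The cost is a small set-up task, a log-in or call per patient, and a protocol amendment. Sample size and analysis are unchanged. The change protects only patients not yet randomised, so it should come before further inclusion.

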### Secondary outcomes

- Success rate of the procedure is described as rate of complete ablations one month after procedure. A complete ablation response is defined as complete absence of enhancing tissue at the tumor site after one month on CT-scan.
- Complications reported as Comprehensive Complication Index (CCI). CCI is a scoring system for overall morbidity and is reflected on a scale from 0 (no complication) to 100 (death). It is based on Clavien-Dindo classification and takes all complications after a procedure into account.
- Highest complication grade according to the Clavien-Dindo Classification
- Wound infections within 30 days is defined as wound dehiscence requiring secondary suturing or treated conservatively. Fascial dehiscence will be recorded separately.

- Postoperative liver failure is defined by the “50-50 criteria” (prothrombin time <50% and serum bilirubin >50 µmol/L on postoperative day five).
- Postoperative pain will be assessed by Visual Analogue Scale for acute and chronic pain, pre-operatively and on each post-operative day until discharge, after seven days, 14 days and one month.
- Overall and disease-free survival.
- Procedure related mortality within 90 days.
- HRQoL before and one month after the procedure will be assessed using the Danish version of The European Organization for Research and Treatment of Cancer Quality of Life (EORTC QLQ C30) and a disease specific form for patients with HCC (QLQ HCC18), cholangio carcinoma (QLQ BIL21) or colorectal liver metastases (QLQ LM21). Depression and anxiety will be assessed before and one month after procedure using PHQ-9 and GAD-7, respectively. Recovery will be assessed with the Quality of recovery (QoR-15) before and seven days after the procedure.
- Length of hospital stay defined as time in days from operation to discharge.
- Blood loss during surgery
- Need for perioperative blood transfusion
- Conversion rate in the laparoscopic group
- Duration of procedure
- Model for Endstage Liver Disease (MELD) and Child-Pugh score before operation and on postoperative day five.
- Patients experiences of undergoing ablation will be explored by individual interviews one months after the procedure.

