##### Sample size

Based on a previous study from our center, the primary outcome (any complication Grade 2 or above, Clavien-Dindo Classification) occurred in 45% of patients undergoing open ablation. The similar complication rate from another external study was 39.5%. The hypothesis is that with a laparoscopic approach, the complication rate can be reduced to 10%. With an alpha of 5% and power of 80%, we will need 60 patients (30 in each arm).

The rate of complete ablation in one month is approximately 95% for open ablations. Using a non-inferior approach and assuming a similar rate of complete ablation in the laparoscopic group, we will need 54 patients (non-inferiority limit 15%, alpha 5% and power 80%).

By including 80 patients, both above sample-size calculations will be covered, and we will have sufficient material compensate for possible excluded patients. Before randomization, we will perform training of laparoscopic ablation using a training fantom developed for the purpose. Accuracy of laparoscopic needle placement with ultrasonography will be assessed using a gel with artificial tumors and an artificial abdominal wall. In addition, we will perform 20 cases with laparoscopic ablation to ensure that technique and learning curve is sufficient compared with our standard of care (open ablation). At this point, sufficient safety and efficacy (comparable to the literature) will be

ensured prior to randomization and additional cases and additional training may be performed is necessary.

After randomization of the first 15 laparoscopic cases, we will perform an interim analysis looking only at conversion rates in the laparoscopic group due to lack of feasibility. In case of a conversion rate above 20%, sample size will be increased according to the conversion rate, e.g. 20% more patients in each group with a conversion rate of 20%. This is done to ensure sufficient power in our comparison between the open and laparoscopic technique.

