## 8. Information from patient records

Patient information will be retrieved from patient electronic charts. Patient characteristics include cancer diagnosis and stage, age, gender, primary liver disease, co-morbidities, MELD-score (patients with HCC), Child Pugh-score (patients with HCC), previous surgery, viral infections and medical comorbidities. Thirty days after the procedure, information regarding success rate of ablation, complications and lengths of stay will be collected from the electronic records. Ninety days after the procedure, procedure related mortality will be recorded. At the end of the study, complete follow-up regarding overall and disease-free survival will be recorded. The collected information will be used to assess primary and secondary outcomes and to assess whether patient characteristics are equally distributed between the two treatment groups.

The primary investigator and sub-investigators have direct access to obtain information in the patient's medical record which is necessary to carry out the research project and for control purposes, including self-control, quality control and monitoring, which they are obliged to carry out.

The information to be used in the project before consent is given from the subjects is passed on to the primary investigator.

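### The one-month CT that decides complete ablation is read outside the study and taken from the chart, with no masking planned and no rule for equivocal enhancement, although near the 15-point limit one reading can change the non-inferiority conclusion.

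*Combined protocol and SAP*

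**What the plan says.** The Aims pair fewer complications with a maintained treatment success rate. Complete ablation is the first secondary outcome: "A complete ablation response is defined as complete absence of enhancing tissue at the tumor site after one month on CT-scan". Sample size gives it a separate non-inferiority calculation. The open rate is stated as follows: "The rate of complete ablation in one month is approximately 95% for open ablations". The calculation continues: "assuming a similar rate of complete ablation in the laparoscopic group, we will need 54 patients", with a 15-point limit, 5% alpha and 80% power.

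The Method section gives the scan its purpose ("at one month all patients will receive a CT-scan to evaluate success rate (complete ablation response") and in the next sentence places it outside the trial: "The CT-scan is part of standard of care, it is assessed by an experienced radiologist, and it is not part of this study".

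Section 8 gives the data route: "Thirty days after the procedure, information regarding success rate of ablation, complications and lengths of stay will be collected from the electronic records". On who does this, Feasibility and timeline says: "The PhD-student will handle inclusion at Rigshospitalet, follow-up, data collection, statistical analyses, and writing of three papers".

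Nowhere in the text supplied is there masking of the CT reader or of the person extracting the result, a study reading form, a second reading, or a rule for equivocal enhancement. Section 4 names Fisher's exact test for dichotomous secondary outcomes and gives no interval method for the non-inferiority comparison. One part of the combined document, just before section 4, was not available for this review.

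**The concern.** The scan supplies an outcome on which the trial intends a formal claim, but the plan does not control how that outcome is produced. A routine report is written for clinical care and need not state the result in the terms of the study definition. Where it does not, someone has to translate it, and the plan says neither who nor by what rule. Nothing prevents the reader or the extractor from knowing the approach.

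In a non-inferiority comparison, residual tumour called complete shrinks the observed difference and makes the claim easier to reach. Failures are expected to be few, so a small number of borderline scans carries much weight. Sections 6 and 14 name lower treatment success as the main possible disadvantage of the laparoscopic approach, so this is the outcome on which a wrong reassurance would matter most.

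**Working it through.** **Inputs.** Open success 95%, laparoscopic success 95%, limit 15 points, alpha 5% and power 80% (Sample size); 40 per arm (Method). The documents do not give misreading rates or a non-inferiority interval method. Both are assumptions here, and a range is shown.

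**Step 1: the plan's own figure.** With unpooled variance and one-sided 5%:

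n per arm = (1.645 + 0.842)² × (0.95×0.05 + 0.95×0.05) / 0.15² = 6.18 × 0.095 / 0.0225 = 26.1, rounded up to 27, so 54 in total. This matches. One-sided 2.5% gives 34 per arm and 68 in total, which does not. The stated alpha is therefore one-sided 5%, used below.

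**Step 2: expected failures.** 40 × 0.05 = 2 per arm.

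**Step 3: where the conclusion flips.** Open is fixed at 38/40. Non-inferiority is met if the lower limit for laparoscopic minus open lies above -15 points.

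- Wald: d - 1.645 × √[pL(1-pL)/40 + pO(1-pO)/40]. For 36/40: -0.05 - 1.645 × √(0.00225 + 0.0011875) = -0.05 - 1.645 × 0.0586 = -0.146. For 35/40: -0.075 - 1.645 × 0.0626 = -0.178.
- Score (Farrington-Manning): the value D at which (d - D)/SE(D) = 1.645, with SE(D) from the rates fitted under a true difference of D.

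| Laparoscopic | Wald | Newcombe | Score |
|---|---|---|---|
| 37/40 | -11.4 | -12.9 | -13.1 |
| 36/40 | -14.6 | -16.0 | -16.2 |
| 35/40 | -17.8 | -19.0 | -19.3 |

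With Wald the flip lies between 36/40 and 35/40. With Newcombe or score it lies between 37/40 and 36/40. The method moves the count, but one scan separates the two conclusions in each case.

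**Step 4: how often a trial ends there.** All pairs of binomial counts at 40 per arm were enumerated, adding the probability of those where changing one laparoscopic reading changes the conclusion.

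| True laparoscopic success (open 95%) | Wald | Newcombe | Score |
|---|---|---|---|
| 95% | 17% | 29% | 30% |
| 90% | 37% | 35% | 36% |

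**Step 5: effect of misreading on a false claim.** Take true laparoscopic success of 80%, exactly at the limit, and open 95%. If a fraction m of residual tumours is called complete, observed success is p + m(1-p).

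- Correct reading: 80% v 95%.
- m = 1/4, laparoscopic arm only: 0.80 + 0.25×0.20 = 85% v 95%.
- m = 1/4, both arms: 85% v 0.95 + 0.25×0.05 = 96.25%.
- m = 1/2, laparoscopic arm only: 90% v 95%. Both arms: 90% v 97.5%.

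| Chance of claiming non-inferiority (score) | Laparoscopic arm only | Both arms |
|---|---|---|
| m = 0 | 4.2% | 4.2% |
| m = 1/4 | 15.2% | 11.4% |
| m = 1/2 | 41.9% | 29.2% |

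With Wald, the laparoscopic-only figures are 7.1%, 23.7% and 57.1%.

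**Step 6: the part due to arm-dependent reading.** At m = 1/4 the rise is 15.2 - 4.2 = 11.0 points. Of this, 11.4 - 4.2 = 7.2 points occur with equal misreading in both arms, and 15.2 - 11.4 = 3.8 points (about a third) depend on the arm. At m = 1/2 the rise is 37.7 points, of which 41.9 - 29.2 = 12.7 depend on the arm.

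**The case against.** A reader might infer that the scans are read unmasked, with the arm known, and that the reading will favour laparoscopy. The documents do not support either inference. They are silent on what the reader knows, and a radiologist with no role in the trial may have no stake in its result. Distrust of a new technique could make reading stricter and push against non-inferiority. What can be said is that no masking is planned.

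Nor do the documents show that the definition will go unapplied. The Method section says the scan is done to assess complete ablation response, and the definition is a single imaging criterion tied to cited reporting standards. That limits reading error, but leaves equivocal enhancement unaddressed.

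A reader might also attribute the whole rise in false claims to lack of masking. Step 6 shows that about two-thirds is plain insensitivity, which masking cannot remove. The misreading rates have no source in the plan. One reading also matters only near the boundary, as for any binary outcome, and the flip point depends on a method the plan does not name.

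Finally, the outcome is secondary, and a routine radiology reading is a defensible pragmatic choice for an 80-patient investigator-initiated trial. These points reduce the weight of the concern. They do not supply the missing rule or remove the gap between a formal non-inferiority aim and an outcome produced outside the study.

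**Conclusion.** The point holds as a gap in outcome ascertainment, not as a demonstrated bias. Near the limit, one scan can change the conclusion. That is the position in about 17% to 30% of trials if both arms reach 95%, and 35% to 37% if laparoscopic success is 90%. If a quarter of residual tumours were called complete, arm-dependent reading would account for 3.8 points of false-claim risk beyond the 11.4% reached with equal misreading. This last figure rests on an assumed misreading rate, a true laparoscopic rate of 80%, one-sided 5% and a score interval. The direction of any real bias is unknown. The change is worth making before results are known, because it is cheap and the claim it protects is half of the hypothesis. The sample size is not affected.

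**What to change.** Replace the Method sentence that puts the scan outside the study. The CT stays standard of care, and no scan or reader is added. Specify that:

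- the radiologist who already reads the scan records each treated tumour as complete or incomplete on a short study form, using the definition under Secondary outcomes;
- the form does not state the approach and is completed before the operation note is opened;
- this form, not later interpretation of the report, is the study outcome, and section 8 is amended to match;
- indeterminate readings follow one prespecified rule in both arms (for example, counted as not complete);
- the way several treated tumours combine into one patient result is stated.

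The cost is protocol wording and about 80 short forms. The arrangement relies on reader compliance at four centers. Masking will be partial, because the abdominal wall on CT may show the incision. The form and the indeterminate rule remain useful even where masking fails, since they replace after-the-fact interpretation of report text.
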